7. STUDY POPULATION

The study will enroll HIV-uninfected individuals who are \geq 15 years old, weight \geq 40 kg, and are candidates to receive TB preventive therapy (i.e. LTBI with no evidence of active TB). The primary target population will be household contacts of newly diagnosed TB patients, recruited from primary care clinics. Analyses of the primary adherence and safety outcomes will be made using data from all enrollees collected through 24 weeks on study.

7.1 Inclusion/Exclusion Criteria

7.1.1 Participant Inclusion Criteria

1) Positive tuberculin skin test or interferon-gamma release assay (IGRA) test and

2) Household contact of an infectious TB case within previous 90 days, defined as sleeping at least once in a residence with a person diagnosed with pulmonary TB; or

3) Documented conversion of TST/IGRA from negative to positive within 2 years

7.1.2 Participant Exclusion Criteria

1) Documented HIV infection

2) Evidence of active tuberculosis on clinical exam or chest x-ray

3) Known intolerance of any study drug

4) Treatment for active or latent TB in the past for more than 14 days

5) Known close contact to someone with INH or rifampin resistant TB

6) Active liver disease or AST/ALT >3 times ULN

7) Neutropenia (ANC <1000)

8) Peripheral neuropathy >Grade 1 by DAIDS Grading Table

9) Pregnant or breastfeeding. Women of childbearing potential must agree to use non-hormonal contraception during study treatment.

10) Weight <40 kg

11) At risk of poor outcome based on clinical judgment and discretion of investigator.

12) Required use of a prohibited medication with a serious drug-drug interaction with rifamycins or isoniazid.

8. ANALYSIS POPULATION

Analyses will be intention-to-treat for both primary outcomes of successful completion and safety, slightly modified in that outcomes will begin being counted from the time of the initial study article dose, which will be supervised by the study staff in clinic.

9. FORMAL INTERIM ANALYSIS

No formal interim analysis for treatment success or safety is planned.

10. STATISTICAL METHODS

10.1 General Considerations

Stata 16.1, R 4.0, and SAS 9.4 or later versions will be used for conducting the main study analyses.

10.2 Outcome Definitions

10.2.1 Treatment completion and successful treatment

1HP

Completion of therapy is defined as having completed 28 daily doses of treatment within 6 weeks. Treatment success is defined as having taken at least 25 doses of medication confirmed by patient report and pill count, and having rifapentine or isoniazid detected at least once in urine or DBS specimens.

3HP

Completion of therapy is defined as having completed at least 12 weekly doses of treatment within 18 weeks. Treatment success is defined as having taken at least 11 doses of medication confirmed by patient report and pill count, and having rifapentine or isoniazid detected at least once in urine or DBS specimens.

Figure 2 shows the algorithm that will be used to classify patients as having treatment success of failure. This hierarchical approach begins with self-reported adherence, then uses pill count, and finally a composite of test results for isoniazid in urine and rifapentine and des-RPT in DBS.

[figure not shown]

Figure 2 Treatment Success

For the treatment success outcome, note that when loss to follow up precludes being able to demonstrate the requisite number of doses having been taken, the outcome is classified as "unsuccessful." A sensitivity analysis will be conducted among those who complete their last scheduled visit after 23 weeks on study.

10.2.2 Safety: Numbers of participants with at least one occurrence of Grade 2 or higher targeted safety events and/or discontinuation of study medications because of side effects attributed to study medications.

Targeted safety events are hypersensitivity syndrome, rash, peripheral neuropathy, hepatotoxicity, nausea and vomiting, and drug-related fever.

This study will grade toxicity and adverse events according to the *Division of AIDS (DAIDS) Table for Grading Adult and Pediatric Adverse Events, Corrected Version 2.1* (dated July 2017).

https://rsc.niaid.nih.gov/sites/default/files/daidsgradingcorrectedv21.pdf See Appendix V of the study protocol.

For the primary safety outcome as of 24 weeks, those who do not complete their last scheduled visit after 23 weeks on study will be considered as failures (safety events).

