Week 2 (+/- 3 days) Day 14

The participant will arrive to clinic at least an hour early, so that everything is in place for drug sampling events to begin on time. Check with the participant about yesterday's HP dosing and to be sure that s/he *did not take today's HP* dose. Check to be sure s/he brought today's HP dose to clinic.

Record the exact time the sample blood and urine was collected. At any time during the events of Day 14 (Week 2 visit) (but before today's dose of HP), conduct the following assessments:

- TB symptom screen
- targeted physical exam
- adverse event assessment
- adherence questionnaire
- pill count of HP, review of medication diary card
- CBC
- chemistry panel including liver function tests
- Dried blood spot and urine collection for drug sampling
- Sampling for NAT2 gene
- urine pregnancy test for participants of childbearing potential

Week4 (+/- 3 days Day 28

The participant will arrive to clinic at least an hour early, so that everything is in place for drug sampling events to begin on time. Check with the participant about yesterday's HP dosing and to be sure that s/he *did not take today's HP* dose. Check to be sure s/he brought today's HP dose to clinic.

Record the exact time the sample blood and urine was collected. At any time during the events of Day 28 (Week 4 visit) (but before today's dose of HP), conduct the following assessments:

- TB symptom screen
- targeted physical exam

- adverse event assessment
- adherence questionnaire
- patient costing survey
- pill count of returned HP, review of medication diary card
- CBC
- chemistry panel including liver function tests
- Dried blood spot and urine collection for drug sampling
- urine pregnancy test for participants of childbearing potential

If participant is assessed to be stable on HP, s/he may take today's dose.

This is the final dose for the 1HP regimen.

Week 8 (+/- 3 days)

Study team will conduct the following assessments:

- TB symptom screen
- targeted physical exam
- adverse event assessment
- urine pregnancy test for participants of childbearing potential

Week 12 (+/- 3 days)

The study team will conduct the following assessments:

- TB symptom screen
- targeted physical exam
- adverse event assessment
- urine pregnancy test for participants of childbearing potential

Week 16 (+/- 3 days)

The study team will conduct the following assessments:

- TB symptom screen
- targeted physical exam
- adverse event assessment

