- Sampling for NAT2 gene
- urine pregnancy test for participants of childbearing potential

Week 8 (+/- 3 days)

Study team will conduct the following assessments:

- TB symptom screen
- targeted physical exam
- adverse event assessment
- adherence questionnaire
- pill count of returned HP, review of medication diary card
- CBC
- chemistry panel including liver function tests
- urine pregnancy test for participants of childbearing potential

Week 12 (+/- 3 days for visit, but not for drug sampling) Day 85 (24 hours after HP dose #12 was taken)

The participant will arrive to clinic at least an hour early, so that everything is in place for drug sampling events to begin on time.

Collect the blood and urine for drug sampling and record the exact time the sample blood and urine was collected.

The study team will conduct the following assessments:

- TB symptom screen
- targeted physical exam
- adverse event assessment
- adherence questionnaire
- patient costing survey
- pill count of returned HP, review of medication diary card
- CBC
- chemistry panel including liver function tests
- Dried blood spot and urine collection for drug sampling
- urine pregnancy test for participants of childbearing potential

This is the final dose for the 3HP regimen.

Week 16 (+/- 3 days)

The study team will conduct the following assessments:

- TB symptom screen
- targeted physical exam
- adverse event assessment

- urine pregnancy test for participants of childbearing potential

Week 24 (+/- 3 days)

The study team will conduct the following assessments:

- TB symptom screen
- targeted physical exam
- adverse event assessment
- urine pregnancy test for participants of childbearing potential
- patient costing survey

This is the final study visit.

12.1.5 Treatment completion and successful treatment.

1HP

Completion of therapy is defined as having completed 28 daily doses of treatment within 6 weeks. Treatment success is defined as having taken at least 25 doses of medication confirmed by patient report and pill count, and having rifapentine or isoniazid detected in urine or DBS specimens.

3HP

Completion of therapy is defined as having completed at least 12 weekly doses of treatment within 18 weeks. Treatment success is defined as having taken at least 11 doses of medication confirmed by patient report and pill count, and having rifapentine or isoniazid detected in urine and DBS specimens.

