15.8.3 Analysis Plan

Analyses will be intention-to-treat for both primary outcomes of successful completion and safety. For the successful completion outcome, losses to follow up (at 4 weeks for Arm 1HP and 12 weeks for Arm 3HP) will be considered as unsuccessful; a sensitivity analysis will be conducted among those not lost in both arms as of 12 weeks. For the safety outcome as of 24 weeks, losses will be considered as failures (safety events).

For the primary outcomes, if fewer than 5% of failures occur in households with 2 or more failures, p-values will be calculated using Fisher's exact test, and 95% confidence intervals (CI) for risk differences will be calculated using the standard asymptotic formula.

Otherwise, within-household correlation will be accounted for using

generalized estimating equations with logit link (for p-value) or identity link (for risk difference CI) and exchangeable correlation structure. If there are convergence problems, a log link function will be used, with delta-method-constructed confidence intervals.

Incidence of active tuberculosis will only be assessed during six months following enrollment but will be evaluated as an exploratory outcome. Incidence will be compared using Kaplan-Meier estimates at 24 weeks and Greenwood's variance formula. This will be a sufficiently rare event that within-household correlation will be ignorable. Censoring will be at last study visit or death. As a sensitivity analysis, TB-free survival will also be analyzed.

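### SAP 10.2.1 limits its sensitivity analysis for treatment success to participants seen after week 23, which discards outcomes already determined and differs, unexplained, from protocol 15.8.3

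*SAP*

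**What the plan says.** SAP 10.2.1 classifies a participant as unsuccessful "when loss to follow up precludes being able to demonstrate the requisite number of doses having been taken". Someone lost after that point keeps the outcome already recorded. The section then adds: "A sensitivity analysis will be conducted among those who complete their last scheduled visit after 23 weeks on study". It is the SAP's only sensitivity analysis of treatment success as a trial outcome; those in 10.3.2 and 10.3.3 concern cost-effectiveness and TB-free survival.

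Protocol 15.8.3 differs. There, "losses to follow up (at 4 weeks for Arm 1HP and 12 weeks for Arm 3HP) will be considered as unsuccessful", and "a sensitivity analysis will be conducted among those not lost in both arms as of 12 weeks". The SAP does not mention or explain the change.

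On timing, protocol 12.1.4 says of the week 4 visit in Arm A, "This is the final dose for the 1HP regimen", and of the week 12 visit in Arm B, "This is the final dose for the 3HP regimen". These visits carry the last adherence questionnaire, pill count, dried blood spot and urine sample. Appendix I (Tables 1A and 1B, the latter labelling the final treatment visit week 11) schedules none of these afterwards. The SAP's completion definitions allow longer: "having completed 28 daily doses of treatment within 6 weeks" for 1HP and "having completed at least 12 weekly doses of treatment within 18 weeks" for 3HP. Protocol 15.2.1 gives 8 and 16 weeks for success.

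**The concern.** The check comes straight after the rule that turns losses into failures, so its natural purpose is to show how far the result depends on that rule. For that, only the outcomes that loss left unknown should change. The week-23 set also removes participants with a documented success, and participants with a documented failure who stopped drug, stayed on study as protocol 12.3.1 asks, and left later.

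If the primary and sensitivity results then differ, the reader cannot tell whether the cause is the scoring of unknown outcomes or the deletion of known ones. The check matters here because SAP section 6 does not inflate the sample size for losses, on the ground that they count as endpoints. The two documents also prescribe different sets, which leaves a choice open that should be settled before outcomes are compared.

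**Working it through.** **1. The plan's own figure.** The documents give no figure for this analysis and no loss rate. The related stated figure is 80% power for 90% v 80% success (SAP section 6). With households of size m = 2 and CV 0.15, households per arm = 1 + (1.96 + 0.842)² × [0.8×0.2/2 + 0.9×0.1/2 + 0.15² × (0.8² + 0.9²)] / 0.1² = 124.7, or 249.4 people; power at 250 per arm is 80.1%. The figure reproduces and concerns the primary analysis, which this point leaves alone.

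**2. Time during which a known outcome can be discarded.**

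| End of treatment used | 1HP, to week 23 | 3HP, to week 23 |
|---|---|---|
| Last treatment visit (4 / 12 weeks) | 19 weeks | 11 weeks |
| Protocol 15.2.1 (8 / 16 weeks) | 15 weeks | 7 weeks |
| SAP completion (6 / 18 weeks) | 17 weeks | 5 weeks |

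**3. Share of randomised participants removed.** Assume loss h per 4 weeks, constant and equal in both arms, counted to week 24, with treatment ending at week 4 or 12.

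- 1HP: unknown = h; known but dropped = (1−h) × [1 − (1−h)⁵]
- 3HP: unknown = 1 − (1−h)³; known but dropped = (1−h)³ × [1 − (1−h)³]

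| h (assumed) | 1HP unknown | 1HP known, dropped | 3HP unknown | 3HP known, dropped |
|---|---|---|---|---|
| 1% | 1.0% | 0.99 × 0.0490 = 4.9% | 3.0% | 0.9703 × 0.0297 = 2.9% |
| 2% | 2.0% | 0.98 × 0.0961 = 9.4% | 5.9% | 0.9412 × 0.0588 = 5.5% |

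Of 250 per arm, that is about 12 v 7 people at 1% and about 24 v 14 at 2%.

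**4. The protocol's week-12 set on the same footing.** Known 1HP outcomes dropped between weeks 4 and 12 are (1−h) × [1 − (1−h)²] = 2.0% at h = 1% and 3.9% at h = 2%. In 3HP the figure is 0.

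**5. When the imbalance disappears.** Let S(t) be the proportion still followed at week t, and let 3HP's loss hazard after week 12 be r times the common hazard λ. Equal numbers of known outcomes are dropped when S(12) × [1 − exp(−11rλ)] = S(4) − S(23). For total loss of 5% to 20% by week 23, r = 1.76 to 1.88. Counting to week 24 as in step 3, r is 1.70 (h = 1%) to 1.74 (h = 2%).

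**6. Effect on the estimate.** Assume 10% loss by week 23, so S(t) = 0.9^(t/23), with primary results of 225/250 and 200/250.

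- Followed to the end of their own regimen: 245.5 in 1HP and 236.6 in 3HP. Success is 225/245.5 = 91.7% and 200/236.6 = 84.5%, a difference of 7.1 points.
- The week-23 set drops a further 20.5 and 11.6 people, leaving 225 per arm. If late loss is unrelated to outcome, the difference is still 7.1 points, on fewer people.
- Extreme bound, low: late losses all successes in 1HP and all failures in 3HP. 204.5/225 − 200/225 = 90.9% − 88.9% = 2.0 points.
- Extreme bound, high: the reverse. 225/225 − 188.4/225 = 100% − 83.7% = 16.3 points.

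**The case against.** **The cut-off has a stated context.** SAP section 7 says the primary outcomes use data collected through 24 weeks, and 10.2.2 uses the same cut-off for safety. It fits the safety outcome. For treatment success, visits after treatment collect no adherence data on participants who kept to schedule, so attending them adds nothing.

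**The 18-week window for 3HP.** Week 24 is the only scheduled visit after that window closes, so a late cut-off could allow for slow completers. Some 3HP participants off schedule at week 12 may indeed have no settled outcome yet. But the longer windows widen the imbalance: at 10% loss the ratio of known outcomes dropped, 1HP to 3HP, goes from about 1.8 (4/12 weeks) to about 2.2 (8/16) and 3.5 (6/18).

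**A common time from enrolment treats the arms alike.** This has some force. Simply excluding those lost before the end of their own regimen conditions on about 4 weeks of retention in one arm and 12 in the other (1.0% v 3.0% excluded at h = 1%). Such an exclusion should not be the main form of the check.

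**Stronger readings that the documents do not support.** A reader might infer that the set necessarily removes more 1HP outcomes. That needs similar loss rates, and none is given. A reader might infer that the check can say nothing about robustness. It does exclude the unknown outcomes scored as failures and, if late loss is unrelated to outcome, it estimates the same difference with less precision. A reader might also infer that restoring the protocol's set is enough; step 4 shows it is not.

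**Conclusion.** The point holds as a defect in a supporting analysis. The week-23 set discards determined outcomes to which the loss-as-failure rule was never applied, and it conflicts without explanation with protocol 15.8.3, whose set has a milder form of the same fault.

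The size is conditional on constant, equal loss: about 4.9% v 2.9% of randomised participants at 1% per 4 weeks, and 9.4% v 5.5% at 2%. The direction is not established; it would level out with late loss in 3HP about 1.8 times that in 1HP, and reverse above that. The range of 2.0 to 16.3 points marks extreme bounds with outcome-dependent loss in opposite directions, not an expected bias. The primary estimate, its p-value and the stated power do not change.

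**What to change.** Put the same text in SAP 10.2.1 and protocol 15.8.3:

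- Keep every participant whose success or failure was determined, whenever they left.
- Vary only the outcomes scored unsuccessful because loss prevented the doses from being documented.
- As the main form, impute those outcomes by arm and give a tipping-point or best/worst-case range.
- If a simple exclusion of those participants is also reported, state that it conditions on different retention times in the two arms.

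Settle this before outcomes are compared by arm. The cost is wording in two documents and slightly more analysis; no new data are needed.

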6. PROTOCOL SUMMARY

Protocol Title:	Treatment Success and Safety of 4 Weeks of Daily Rifapentine and Isoniazid (1HP) vs. 12 weeks of Weekly Rifapentine and Isoniazid (3HP) for Prevention of Tuberculosis in HIV-uninfected Individuals (1v3HP for TPT in HIV-uninfected individuals): Ultra Curto
Treatment Indication:	TB preventive treatment (TPT) in HIV uninfected persons age ≥15 years with LTBI
Trial Objective:	To compare treatment success (adherence and completion of treatment) and safety of 1HP with 3HP in HIV-uninfected adults and adolescents at increased risk of TB.
Trial Design:	An international, multicenter, randomized, controlled, open-label, two arm, Phase IV clinical trial. Arm A (n=250) : Experimental arm. Rifapentine 600 mg daily and isoniazid 300 mg daily for 4 weeks
	Arm B (n=250) : Control arm. Rifapentine 900 mg and isoniazid 900 mg weekly for 12 weeks.
Sample Size	500
Patient Population:	The study will enroll HIV-uninfected individuals who are ≥ 15 years old, and are candidates to receive TB preventive therapy (i.e. LTBI with no evidence of active TB). Key exclusion criteria include HIV infection, abnormal liver enzymes, neutropenia, previous treatment of TB or latent TB infection, or a history of study drug intolerance.
Study treatment:	TB preventive treatment: Arm A (n=250) : Experimental arm. Rifapentine 600 mg daily and isoniazid 300 mg daily for 4 weeks. Arm B (n=250) : Control arm. Rifapentine 900 mg weekly and isoniazid 900 mg weekly for 12 weeks.
Trial sites:	 Health units from Rio de Janeiro Health Secretariat and NARDOT study slinis, Rio de Janeiro, Brazil

Criteria for evaluation:

Primary Objectives:

To compare treatment success (completion of treatment with \geq 90% adherence) of 1HP compared with 3HP in HIV-uninfected adults and adolescents at increased risk of TB.

To compare the safety of 1HP vs 3HP in HIV-uninfected adults and adolescents at increased risk of TB.

Primary Outcomes:

(1) Successful completion of TPT with \geq 90% adherence documented by self-report, pill count, and pharmacologic monitoring.

(2) Safety of treatment regimens, defined as occurrence of Grade 2 or higher targeted safety events while taking study medications or within 14 days of stopping, or discontinuation of study medications because of side effects.

Targeted safety events are hypersensitivity syndrome, rash, peripheral neuropathy, hepatotoxicity, nausea and vomiting, and drug-related fever.

Secondary Outcome:

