15.2 Study Outcomes

15.2.1 Primary Outcomes

(1) Successful completion of TBT with ≥90% adherence documented by self-report, pill count, and pharmacologic monitoring.

Definitions:

For 1HP, successful completion of TPT is defined as having taken at least 25 doses of self-administered daily medication within 8 weeks of enrollment confirmed by patient report and pill count, and having rifapentine or isoniazid detected in urine and DBS specimens.

For 3HP, successful completion of TPT is defined as having taken at least 11 doses of self-administered weekly medication within 16 weeks as confirmed by patient report and pill count and having rifapentine or isoniazid detected in urine and DBS specimens.

(2) Safety of treatment regimens, defined as occurrence of Grade 2 or higher targeted safety events and discontinuation of study medications because of side effects.

Targeted safety events are hypersensitivity syndrome, rash, peripheral neuropathy, hepatotoxicity, nausea and vomiting, and drug-related fever.

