In the BRIEF TB trial the rate of targeted safety events was 3%. We would want to demonstrate a reduction from 13% to at least as low as 6% in HIV-negative patients. With a CV of 0.1 (again, in reference to the maximum entropy distribution for the corresponding proportions, which are lower here than for the previous outcome), and the sample size of 250 individuals (about 125 households) in each study arm, we will have about 80% power for detecting a significant difference at a two-sided 0.05 significance level. We would also have 80% power to distinguish between risks of 12% and 5% in the two study arms. Although for convenience we have phrased this in terms of an hypothesis test, our goal is to estimate the difference in safety risks. With this sample size, and risks of 13% and 6% with 3HP and 1HP, respectively, the 95% CI for the risk difference will have a half-width of 3 percentage points. Reporting this CI will enable readers to make their own conclusions regarding non-inferiority of 1HP with respect to 3HP, in addition to superiority. (Dunn 2018)

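### The primary safety outcome has no single event window, and no safety analysis is planned that leaves out the events imputed for missed final visits

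*SAP*

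**What the plan says.** The documents describe the co-primary safety outcome in three ways.

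- **Treatment plus 14 days.** Protocol 6 and 8.2 count Grade 2 or higher "targeted safety events while taking study medications or within 14 days of stopping", or discontinuation for side effects.
- **No window.** Protocol 15.2.1 and 15.3 and SAP 3.2 give the outcome as "occurrence of Grade 2 or higher targeted safety events and discontinuation of study medications because of side effects". The definition that opens SAP 10.2.2 has no time limit either.
- **24 weeks, with loss scored as an event.** Protocol 15.8.3: "For the safety outcome as of 24 weeks, losses will be considered as failures (safety events". SAP 10.2.2 makes the rule specific: "those who do not complete their last scheduled visit after 23 weeks on study will be considered as failures (safety events". SAP 7 agrees on the horizon: "Analyses of the primary adherence and safety outcomes will be made using data from all enrollees collected through 24 weeks on study".

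Both loss sensitivity analyses belong to treatment success. Protocol 15.8.3 has "a sensitivity analysis will be conducted among those not lost in both arms as of 12 weeks", attached to the successful-completion outcome. SAP 10.2.1 has "A sensitivity analysis will be conducted among those who complete their last scheduled visit after 23 weeks on study", again for treatment success. Neither document plans one for safety. SAP 6 says of this outcome that "our goal is to estimate the difference in safety risks".

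**The concern.** No section says which window governs. On schedule, treatment plus 14 days ends at about week 6 in 1HP and week 13 to 14 in 3HP. A 24-week window therefore adds about 18 off-drug weeks in 1HP and about 10 in 3HP. Two cases show the consequence:

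- A 1HP participant finishes at week 4 and has a Grade 2 rash at week 15. This is an event to 24 weeks and not an event under the 14-day limit.
- A 1HP participant is seen event-free at weeks 8, 12 and 16 and has no final visit. This is a failure under SAP 10.2.2, although the whole 14-day window was observed without an event.

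The SAP's introduction says it aims to avoid data-driven analysis, and an undefined window on a co-primary outcome leaves a choice open after the data are seen. Separately, the reported difference will mix observed toxicity with imputed events, and no planned analysis shows how much is which. The Protocol's rationale names the safety of 1HP in people without HIV as the open question, and SAP 6 invites readers to judge non-inferiority from this confidence interval.

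**Working it through.** **Inputs.** 250 per arm; risks 13% (3HP) and 6% (1HP); two-sided 0.05 (Protocol 15.4, SAP 6). Neither document gives a loss rate, so every loss figure below is an assumption, with loss taken as independent of events. Clustering is ignored; at the plan's CV of 0.1 it changes power by less than half a point.

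**Method.** Pooled two-proportion test: power = Φ((d − 1.96·s0)/s1), where d is the risk difference, s0 = √(2·p̄(1−p̄)/n) and s1 = √((p1(1−p1)+p2(1−p2))/n). With loss m scored as failure, the observed risk is 1 − (1−p)(1−m).

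**The plan's own figure.** For 13% v 6%: s0 = 0.02623, s1 = 0.02604, so (0.07 − 0.0514)/0.02604 = 0.71 and power is 76%. The plan says about 80%. Its companion case, 12% v 5%, does reproduce (80.3%). The comparisons below start from 76%.

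**Equal loss under the SAP rule.**

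| Loss in each arm | 3HP v 1HP | Difference (points) | Power |
|---|---|---|---|
| 0% | 13.0% v 6.0% | 7.0 | 76% |
| 3% | 15.6% v 8.8% | 6.79 | 64% |
| 5% | 17.35% v 10.7% | 6.65 | 57% |
| 10% | 21.7% v 15.4% | 6.3 | 44% |

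At 5% loss, the imputed share of all counted events is 0.05 × 0.87/0.1735 = 25% in 3HP and 0.05 × 0.94/0.107 = 44% in 1HP. With equal true risks and equal loss, the observed risks stay equal and type I error stays at 5%.

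**Unequal loss under the SAP rule.**

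- True risks 10% in both arms, loss 5% v 3%: observed 14.5% v 12.7%; chance of a significant result 9%.
- True risks 10% in both arms, loss 10% v 5%: observed 19.0% v 14.5%; chance 27%.
- True 13% v 6%, loss 5% in 3HP and 10% in 1HP: observed 17.35% v 15.4%; difference 2.0 points, power 9%.

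None of these figures depends on which event window is chosen. They would be the same under a plain 24-week outcome.

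**Completers only.** At 5% loss, 0.95 × 250 = 237.5 per arm. The difference stays at 7.0 points and power is 74%.

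**Loss scored as an event only inside each arm's own 14-day window.** Take loss at a constant rate to 5% by week 24 and windows closing at weeks 6 and 13. Loss before closure is 1 − 0.95^(6/24) = 1.27% in 1HP and 1 − 0.95^(13/24) = 2.74% in 3HP.

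- True 13% v 6%: observed 15.38% v 7.20%, a difference of 8.2 points instead of 7.0.
- True 10% in both arms: observed 12.47% v 11.15%; type I error about 7%. At 10% loss by week 24 it is 14.99% v 12.34% and about 14%.

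Both shifts favour 1HP, because 3HP is exposed to loss for longer.

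**The case against.** The strongest defence is that the analysis sections agree. The loss rule appears only in Protocol 15.8.3 and SAP 10.2.2, and both set it against an outcome as of 24 weeks. SAP 7 uses the same horizon, and Protocol 13.3.6 collects adverse events to the end of follow-up. Scoring missing as failure is a recognised convention for such an outcome; it is pre-specified, and it runs to the same week in both arms. All of that stands.

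Three stronger readings are tempting, and the documents do not support them.

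- A reader might infer that the plan combines the 14-day definition with the week-24 loss rule. No section does so. Protocol 6 and 8.2 are the outliers.
- A reader might take the loss of power and the 9% and 27% figures as the cost of the window conflict. They measure missing = failure under any window.
- A reader might expect substantial loss. The documents give no rate. They do plan reminders, calls and home visits (Protocol 10.3), compensation (18.7), follow-up after stopping drug (12.3.1, 14.4.2) and out-of-window visits with full procedures (12.3.9). SAP 10.2.2 sets no upper limit on the final visit, so a late one need not count as lost.

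Reading 24 weeks as only a data cut-off does not settle the matter. The SAP never restates the 14-day limit, and it ties failure to the final visit itself. Nor does the defence supply a safety analysis without imputed events.

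**Conclusion.** The point holds as an inconsistent definition and a missing analysis, and it should be fixed. It is a cheap improvement and does not invalidate the design. The window conflict is established by the text alone. Its numerical effect depends on how many targeted events occur off drug, which the documents do not give.

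The loss rule keeps nominal type I error when loss is equal and mainly costs power: 76% falls to 64%, 57% and 44% at 3%, 5% and 10% loss. Unequal loss can create or hide a difference. These sizes rest on assumed loss rates, 250 per arm, no clustering, and loss independent of events. As written, the plan cannot separate toxicity from missed visits in the difference it sets out to estimate.

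**What to change.** 1. State one event window for the safety outcome and use it in Protocol 6, 8.2, 15.2.1, 15.3 and 15.8.3 and in SAP 3.2, 7 and 10.2.2. The analysis sections already work to 24 weeks, so the smallest change is to amend Protocol 6 and 8.2 to match.
2. Pre-specify a safety analysis without imputed events, either observed events only or week-24 completers as SAP 10.2.1 does for treatment success. Report observed and imputed events separately by arm.
3. If the 14-day window is kept instead, do not make loss = event inside each arm's own window the main rule, given the bias towards 1HP shown in the working. Use observed events as the main analysis and loss = event as a sensitivity analysis.

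The cost is Protocol and SAP wording plus one analysis, with no new visits. If 24 weeks is kept, late loss stays counted as toxicity in the main result, which is why item 2 is needed.
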